7.6. Treatment Compliance

7.6.1. Part A

Compliance with administration of double-blind study treatment in the clinic at Visits 4 and 6 will be monitored by capturing the date that the participant ingested the double-blind study treatment at each of these visits. If a scheduled ingestion does not occur, the sponsor must be notified and the reason captured in the eCRF.

Compliance with study treatment dosing by the participant outside of the clinic will be monitored by counting the number of tablets dispensed and returned. Before dispensing new study treatment, study center personnel will make every effort to collect all unused study treatment and empty bottles. If a participant demonstrates poor compliance at any time during the study (< 80% or > 120% measured by pill counts), the investigator should evaluate whether the participant should be discontinued from the study.

The study centers will keep an accurate drug disposition record that specifies the amount of study treatment administered to each participant and the date of administration.

7.6.2. **Part B**

Site staff personnel will administer morning and afternoon doses of double-blind study treatment to the participant during the inpatient double-blind treatment period (Visit 3 [Day 1] through Visit 10 [Day 8]) each day and will capture the date and time the participant ingested each dose. If a scheduled ingestion does not occur, the reason must be captured in the eCRF.

During the outpatient double-blind treatment period, participants will be instructed by site staff to try to adhere to the relative dosing times used within the inpatient phase (ie, morning and afternoon doses, approximately 8 hours apart). Should a dose not be administered accordingly, the participant should be instructed as per Section [7.2](#).

During the 2nd week of the outpatient double-blind treatment period from Visit 10 (Day 8) afternoon dose through Visit 12/ET (Day 14/ET), participants will be instructed to record the date and time of the morning and afternoon dose and any missed doses on the Study Medication Dosing Log in the Patient Diary on each day. The participant will be instructed to bring the study medication bottle to the clinic at Visit 11 and at Visit 12/ET. The outpatient dosing compliance will be monitored by site staff personnel at Visit 11 (Day 11) and Visit 12/ET (Day 14/ET) by reconciling the number of tablets in the bottle at each visit and by reviewing the dosing log in the Patient Diary (see Section [5.1.2](#)).

Study center personnel will make every effort to collect all unused study treatment and empty bottles on Visit 12/ET (Day 14/ET). If a participant demonstrates poor compliance at any time during the study (< 80% or > 120% measured by pill counts), the investigator should evaluate whether the participant should be discontinued from the study.

The study centers will keep an accurate drug disposition record that specifies the amount of study treatment administered to each participant and the date of administration.

7.7. **Concomitant Therapy**

The use of any concomitant medication, prescription or over-the-counter, is to be recorded on the participant's eCRF at each visit along with the reason the medication is taken.

7.7.1. Prohibited Treatments

Participants must discontinue any of the medications listed below for the specified period prior to baseline. These medications are prohibited for the duration of the study. Other medications being used at Screening may be continued.

The following medications are prohibited:

- Antipsychotics
- Antidepressants
- Stimulants
- Anticonvulsants/mood stabilizers
- Dopamine-releasing drugs or dopamine agonists
- Psychotropic drugs not otherwise specified (including herbal products, such as St. John's Wort, and certain nutritional supplements)

See [Appendix 6](#) Concomitant Medications for a comprehensive list of prohibited medications and allowed medication usage. Appropriate washout of prohibited medications is to be conducted at the discretion of the investigator and should begin as soon as practical following consent and Screening.

The decision to administer a prohibited medication/treatment during the study period is done with the safety of the study participant as the primary consideration. When possible, the sponsor is to be notified before the prohibited medication/treatment is administered.

7.7.2. Permitted Treatments

Any medication or vaccine (including over-the-counter or prescription medicines, vitamins, and/or herbal supplements) that the participant is receiving at the time of enrollment or receives during the study must be recorded along with:

- Indication
- Dates of administration including start and end dates
- Dosage information including dose and frequency

Therapy considered necessary for the participant's welfare may be given at the discretion of the investigator. If the permissibility of a specific medication/treatment is in question, please contact the sponsor.

The sponsor or designee should be contacted if there are any questions regarding concomitant or prior therapy.

For Insomnia

Eszopiclone, zolpidem, zolpidem extended-release, zopiclone, or zaleplon for insomnia may be continued provided the medication has been used in a consistent manner for 4 weeks prior to enrollment. Following enrollment, these medications may also be introduced in participants not previously treated as necessitated by insomnia that emerges or worsens during the study. In these participants, the medications will be permitted up to 3 times a week, as follows:

Part A—not permitted within 8 hours of psychiatric or neurological measures

Part B—not permitted within 12 hours of psychiatric or neurological measures or a scheduled qEEG/ERP measurement

The medications are permitted at the following doses:

- Zolpidem (maximum of 10 mg/day)
- Zolpidem extended release (maximum of 12.5 mg/day)
- Zaleplon (maximum of 20 mg/day)
- Eszopiclone (maximum of 3 mg/day)
- Zopiclone (maximum of 7.5 mg/day)
- Suvorexant (maximum of 10 mg/day)

These medications must be administered before bedtime as recommended in their prescribing information. The medication must be documented on the concomitant medications page of the eCRF. No such medication is permitted within 8 hours (Part A) or within 12 hours (Part B) of psychiatric or neurological assessments or a scheduled qEEG/ERP measurement.

For Anxiety or Agitation

Episodic use of benzodiazepines up to approximately 2 mg/day lorazepam equivalent dose and for up to 3 consecutive days at a time may be given for anxiety-related conditions and agitation (not permitted within 8 hours of psychiatric or neurological assessments [Part A] or not permitted within 12 hours of psychiatric or neurological assessments or a scheduled qEEG/ERP measurement [Part B]).

7.8. Treatment after the End of the Study

Participants whose MDD symptoms worsen or are determined by the investigator not to be adequately controlled prior to completing the double-blind treatment period will be allowed to discontinue the study and start appropriate treatment at the investigator's discretion. This new treatment will not be provided by the sponsor.

8. Discontinuation/Withdrawal Criteria

Notification of early participant discontinuation from the study and the reason for discontinuation will be made to the sponsor and will be clearly documented on the appropriate case report form.

Reasons for discontinuation from the study treatment and/or the study may include the following:

- Adverse event
- Lack of efficacy
- Lost to follow-up
- Non-compliance with study drug
- Other
- Pregnancy
- Protocol deviation
- Screen failure
- Site terminated by sponsor
- Study terminated by sponsor
- Withdrawal by subject (withdrawal of consent to participate in the study)

8.1. Discontinuation of Study Treatment

All randomized participants who prematurely discontinue from the study, regardless of cause, should be seen for a final assessment at an ET Visit. A final assessment will be defined as completion of the evaluations scheduled for all participants at the Follow-Up Visit. Participants who prematurely discontinue from the study before completing 2 weeks of double-blind treatment should enter the 1-week safety follow-up period.

Any participant may be withdrawn due to AE at the discretion of the investigator.

Any participant who meets any of the following criteria at any point during the study must be withdrawn from participation, due to AE(s) related to suicide:

- a. A suicide attempt
- b. Significant risk, as judged by the investigator, based on the psychiatric interview or information collected in the C-SSRS
- c. MADRS Item 10 score ≥ 5

In the event that a participant is withdrawn for a suicide-related AE, the participant should be referred for additional treatment or hospitalization, as clinically indicated, in addition to withdrawing the participant from the study.

Discontinuation of study treatment for abnormal liver function (criteria for potential Hy's law described in Section 9.2.6) should be considered by the investigator if the investigator believes that it is in best interest of the participant.

If a clinically significant finding is identified after enrollment, the investigator or qualified designee will determine if the participant can continue in the study and if any change in participant management is needed. Any new clinically relevant finding should be reported as an AE. Clinically significant findings upon termination should be followed until the condition returns to prestudy status or can be explained as unrelated to study treatment. If necessary, additional follow-up visits may be scheduled.

See the schedule of activities (Section 2.1 [Part A] and Section 2.2 [Part B]) for data to be collected at the ET visit and the Safety Follow-Up Visit.

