2.1. Part A

		Double-blind Treatment Period					Safety Follow-up Period
		2	3	4	5	6/ET ^a	
Visit	Screening (I)	2	3	4	5	6/ET ^a	7
Study Day	up to -14 days	1	2	8	9	15	22
Informed consent	x						
Medical (surgical, neurologic) and psychiatric histories	x						
Prior medication history	x						
Inclusion/exclusion	x	x					
Randomization assessment		x					
Clinical laboratory determinations ^b	x	x				x	
Urine drug screen	x					x	
Serum pregnancy test	x					x	
Pharmacogenomics consent and sample ^c				x			
Vital signs ^d	x	x	x	x	x	x	x
ECG	x					x	
Physical examination	x					x	
SCID	x						
MADRS	x	x	x	x	x	x	x
CGI-S	x	x	x	x	x	x	

		Double-blind Treatment Period					Safety Follow-up Period
		2	3	4	5	6/ET ^a	
Visit	Screening (1)	2	3	4	5	6/ET ^a	7
Study Day	up to -14 days	1	2	8	9	15	22
BPRS+	x		x	x	x	x	
CADSS	x		x	x	x	x	
C-SSRS	x	x	x	x	x	x	x
HAM-A ^c		x	x	x		x	
AEs		x	x	x	x	x	x
Concomitant medications	x	x	x	x	x	x	x
Study treatment administration in the clinic		x		x			
Study treatment compliance		x		x	x	x	

Screening procedures may be conducted on up to 2 separate dates where necessary to accommodate participant and site schedule; however, every effort should be made to conduct all procedures as early as possible in the screening period.

If necessary, study visits may be conducted up to 2 days before or after the scheduled visits except for visits that are 1 day apart (ie, Visits 2 and 3 must be conducted 1 day apart, and Visits 4 and 5 must be conducted 1 day apart).

^a Performed for all participants, including those prematurely discontinued after randomization. Clinically significant findings upon termination should be followed until the condition returns to prestudy status or can be explained as unrelated to study treatment. If necessary, additional follow-up visits can be scheduled.

^b Participants will be requested to fast overnight or for at least 8 hours before arriving at the study center for appointments involving the collection of clinical laboratory blood tests. Clinical laboratory tests can be done at any visit for safety reasons at the discretion of the investigator.

^c A separate ICF must be signed before the pharmacogenomic blood sample is taken. Participation is optional. This ICF may be signed at any visit during the study; however, the sample should be collected at any visit after the participant has been randomized.

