8.2. Withdrawal from the Study

- A participant may withdraw from the study at any time at his/her own request, or may be withdrawn at any time at the discretion of the investigator for safety, behavioral, compliance, or administrative reasons.
- If the participant withdraws consent for disclosure of future information, the sponsor may retain and continue to use any data collected before such a withdrawal of consent.
- If a participant withdraws from the study, he/she may request destruction of any samples taken and not tested, and the investigator must document this in the site study records.
- See the schedule of activities for data to be collected at the time of study discontinuation and follow-up and for any further evaluations that need to be completed.

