8.3. Lost to Follow Up

A participant will be considered lost to follow-up if he or she repeatedly fails to return for scheduled visits and is unable to be contacted by the study site.

The following actions must be taken if a participant fails to return to the clinic for a required study visit:

- The site must attempt to contact the participant and reschedule the missed visit as soon as possible and counsel the participant on the importance of maintaining the assigned visit schedule and ascertain whether or not the participant wishes to and/or should continue in the study.

- Before a participant is deemed lost to follow up, the investigator or designee must make every effort to regain contact with the participant (where possible, 2 telephone calls, and if necessary, a certified letter to the participant's last known mailing address or local equivalent methods). These contact attempts should be documented in the participant's medical record.
- Should the participant continue to be unreachable, he or she will be considered to have withdrawn from the study with a primary reason of lost to follow-up.

9. Study Assessments and Procedures

- Study procedures and their timing are summarized in the schedule of activities (Section 2.1 [Part A] and Section 2.2 [Part B]).
- Protocol waivers or exemptions are not allowed.
- Immediate safety concerns should be discussed with the sponsor immediately upon occurrence or awareness to determine if the participant should continue or discontinue study treatment.
- Adherence to the study design requirements, including those specified in the schedule of activities, is essential and required for study conduct.
- All screening evaluations must be completed and reviewed by the investigator or qualified designee to confirm that potential participants meet all eligibility criteria. The investigator will maintain a screening log to record details of all participants screened and to confirm eligibility or record reasons for screening failure, as applicable.
- Procedures conducted as part of the participant's routine clinical management (eg, blood count) and obtained before signing of the ICF may be utilized for screening or baseline purposes provided the procedure met the protocol-specified criteria and were performed within the time frame defined in the schedule of activities.
- Repeat or unscheduled blood samples may be taken for safety reasons or for technical issues with the samples.

Diagnostic Assessments

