9.4.1. Physical Examinations

A complete physical examination will be performed at Screening and at Visit 6/ET (Part A) or at Screening and Visit 12/ET (Part B) by a professionally trained physician or health professional listed on Form FDA 1572 and licensed to perform physical examinations.

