9.4.3. Electrocardiograms

A 12-lead ECG will be performed at Screening and Visit 6/ET (Part A) and at Visit 1 (Screening), Visit 12/ET (Day 14/ET), and Visit 14 (Day 21) (Part B). ECGs will be performed and electronically transmitted to a central ECG laboratory for analysis according to the instructions provided by the central ECG laboratory. Measurements (in msec) will be recorded for the following parameters: PR interval, QRS duration, and uncorrected QT interval. QTcB (Bazett corrected QT interval) and QTcF (Fridericia corrected QT interval) will be calculated.

The overall interpretation and determination of the clinical relevance of ECG findings using the central ECG interpretation laboratory report will be the responsibility of the investigator and will be recorded in the participant's eCRF.

Throughout the study, the investigator will review the central ECG reports and indicate the clinical significance of all abnormal values, and then sign and file the report in the participant's study file. In case of any abnormal ECG finding, unscheduled ECGs may be conducted at the discretion of the PI.

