12.2. Appendix 2: Clinical Laboratory Tests

Blood and urine samples for clinical laboratory tests will be collected as listed in the schedule of activities (Section 2.1 [Part A] and Section 2.2 [Part B]).

A central laboratory will be used to evaluate all urine and blood samples, which will be collected, processed, and stored according to the instructions provided by the laboratory.

During screening, the investigator will assess the clinical significance of any values that are outside the reference ranges provided by the central laboratory; participants with abnormalities judged to be clinically significant will be excluded from the study.

Participants will be asked to fast overnight or for at least 8 hours before arriving at the study center for appointments involving the collection of clinical laboratory blood tests.

For Part A and Part B, the following clinical laboratory levels will be measured at Screening only:

Clinical laboratory screening tests: HbA1c, fasting insulin, TSH, T3, and free T4

Hepatitis screening: HCV antibody, hepatitis-B surface antigen, and hepatitis-B core antibody total will be tested. Reflex hepatitis-B core antibody IgM will be performed for all hepatitis-B core antibody total positive or reactive results. Positive test results will be sent for confirmation testing.

The following clinical laboratory levels will be measured at Screening, Visit 2, and Visit 6/ET (Part A) and at Screening, predose at Visit 9 (Day 7), Visit 12/ET (Day 14/ET), and Visit 14 (Day 21) (Safety Follow-Up) (Part B) unless otherwise noted:

Hematology:	Absolute and differential white blood cell count, erythrocyte count, hemoglobin, hematocrit, platelet count, and red blood cell indices (mean corpuscular volume, mean corpuscular hemoglobin, and mean corpuscular hemoglobin concentration)
Chemistry:	Sodium, potassium, calcium, chloride, bicarbonate, magnesium, gamma glutamyl transferase, phosphate, glucose, blood urea nitrogen, creatinine, creatine phosphokinase, total protein, alkaline phosphatase, albumin, bilirubin (total; direct; indirect), ALT, AST, total cholesterol, low-density lipoprotein, high-density lipoprotein, triglycerides ^a
Urinalysis:	Specific gravity, pH, protein, glucose, ketones, and blood
UDS:	Benzoylecggonine (cocaine), barbiturates, amphetamines, benzodiazepines, cannabinoids, opiates, methadone, phencyclidine
Pregnancy (Part A):	Serum β -hCG at Screening and Visit 6/ET

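### Protocol 8.1 defines the early-termination assessment by the Follow-Up Visit, which in Part A omits 10 of the 15 Visit 6/ET evaluations, including liver tests and ECG; the 9.4.4 liver retest rule also lists a non-elevated alkaline phosphatase

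*Protocol*

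**What the plan says.** **Early termination.** Protocol 8.1 requires a final assessment at an ET visit for all randomized participants who stop early, whatever the cause. It then says: "A final assessment will be defined as completion of the evaluations scheduled for all participants at the Follow-Up Visit". The same section ends by sending the reader to the schedule of activities "for data to be collected at the ET visit and the Safety Follow-Up Visit", so it treats these as two separate visits.

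The Part A schedule (Section 2.1) has a combined Visit 6/ET column, and footnote a says of it: "Performed for all participants, including those prematurely discontinued after randomization". Sections 9.4.1 (physical examination) and 9.4.3 (ECG) place the last Part A assessment at Visit 6/ET. Appendix 2 does the same for laboratory tests. None of the three mentions Visit 7.

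**Liver retest.** Section 9.4.4 calls for an unscheduled retest on ALT or AST at or above 3 x ULN, total bilirubin at or above 2 x ULN, and/or alkaline phosphatase below 2 x ULN, with a pointer to 9.2.6. Section 9.2.6 uses the same three thresholds, joined by AND, to define a potential Hy's law case. SAP 11.5.2 describes the alkaline phosphatase condition as non-elevated. Footnote h of the Part B schedule (Section 2.2) sends sites to 9.4.4 and Appendix 2 for retest details.

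**The concern.** Section 8.1 is where a site looks when a participant discontinues, and its sentence is an explicit definition that names the wrong visit. A Part A site taking it literally would do the short follow-up set at the ET visit, and the same short set again a week later in the safety follow-up period. It would draw no liver panel and record no ECG on either occasion.

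Those who stop for an adverse event are in this group. The liver was a target organ in dogs (Protocol Section 3), and Part A admits AST or ALT up to 2 x ULN, against 1.5 x ULN in Part B (exclusion 28). The tables would be affected too. The percentages of potentially clinically significant laboratory and ECG values count only participants with at least one postbaseline assessment (Protocol 10.3.5.2 and 10.3.5.4; SAP 11.2 and 11.4), so an untested discontinuer drops out of them.

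In 9.4.4, a condition that normal results satisfy cannot work as a retest trigger on its own. If it is joined by AND, the trigger shrinks to full potential Hy's law cases.

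**Working it through.** **Step 1. Count the Part A evaluations** (Protocol 2.1; the SAP copy, Table 4-1, agrees).

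- Visit 6/ET, 15 rows marked: laboratory tests, urine drug screen, pregnancy test, vital signs, ECG, physical examination, MADRS, CGI-S, BPRS+, CADSS, C-SSRS, HAM-A, AEs, concomitant medications, treatment compliance.
- Visit 7, 5 rows marked: vital signs, MADRS, C-SSRS, AEs, concomitant medications. All five are among the 15.
- Difference: 15 - 5 = 10, namely laboratory tests, urine drug screen, pregnancy test, ECG, physical examination, CGI-S, BPRS+, CADSS, HAM-A and compliance.
- Of these 10, the first five are not scheduled at Visits 3, 4, 5 or 7. Taking the Visit 2 laboratory draw as the baseline sample, they have no other scheduled measurement after dosing begins.

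The optional pharmacogenomic sample is left out because it is tied to no particular visit. Counting it at both visits would give 6 of 16. HAM-A applies only to participants who entered after the amendment was approved, and the pregnancy test only to women of childbearing potential, so 15 is the full column and not a count for every person.

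**Step 2. Part B.** There are two follow-up visits (Visits 13 and 14), so the wording in 8.1 does not identify one. If Visit 14 is meant, laboratory tests and ECG are included (Appendix 2, 9.4.3). The physical examination is at neither visit (9.4.1). The loss of liver panel and ECG is therefore a Part A problem.

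**Step 3. Participants whose ET visit falls under both rules.** The documents give no dropout or ET attendance rate. Assume 5% to 15% stop early and 50% to 100% of those attend an ET visit.

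- All arms (100): 100 x 0.05 x 0.5 = 2.5 to 100 x 0.15 x 1.0 = 15.
- Active arms (75): 75 x 0.05 x 0.5 = 1.9 to 75 x 0.15 x 1.0 = 11.25.

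**Step 4. Test the 9.4.4 trigger** on illustrative values in multiples of ULN. When all three conditions are joined by AND, the trigger is identical to 9.2.6.

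| ALT/AST | Bilirubin | Alk. phos. | 9.4.4 read as OR | 9.4.4 read as AND (= 9.2.6) |
|---|---|---|---|---|
| 1 | 0.5 | 0.8 | met | not met |
| 1 | 0.5 | 3 | not met | not met |
| 5 | 0.5 | 0.8 | met | not met |
| 5 | 0.5 | 3 | met | not met |
| 1 | 3 | 0.8 | met | not met |
| 1 | 3 | 3 | met | not met |
| 5 | 3 | 0.8 | met | met |
| 5 | 3 | 3 | met | not met |

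Read as OR, a normal panel (row 1) triggers a retest, while an isolated alkaline phosphatase rise (row 2) is the only combination that does not. Read as AND, an isolated ALT or AST of 5 x ULN is not named at all. Neither reading gives a sensible threshold.

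**The case against.** The strongest reply is that the two ET rules can both be satisfied. The five Visit 7 evaluations lie within the 15, so a site that completes the ET column meets the 8.1 sentence as well, and that sentence does not say that only those evaluations are to be done. The rest of the protocol points the same way. Section 8.2 says: "See the schedule of activities for data to be collected at the time of study discontinuation and follow-up". Section 9 says: "Adherence to the study design requirements, including those specified in the schedule of activities, is essential and required for study conduct", and it bars waivers. Skipping the liver panel or ECG at an ET visit would be a deviation whatever 8.1 says. Investigators may also order laboratory tests and ECGs at any time (Section 2.1 footnote b; Section 9.4). Section 9.3 reports no liver findings in healthy volunteers given 50 mg for 10 consecutive days, twice the top Part A dose.

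On 9.4.4, the clause sits with text about clinically significant abnormal values, and footnote a of Appendix 2 repeats abnormal liver tests in any case. It is hard to picture a site retesting a normal panel.

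All of this stands as a limit on the consequence: omission is possible but is not the expected outcome. It does not make either sentence right. A definition that names the wrong visit is still wrong when a careful reader can work around it, and a retest rule should not depend on the reader ignoring one of its criteria.

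**Conclusion.** The concern holds, as a minor one. Section 8.1 defines the ET assessment by a visit that in Part A carries 5 of the 15 Visit 6/ET evaluations. Of the 10 left out, 5, including the liver panel and ECG, have no other scheduled measurement after dosing begins. In Part B the reference is ambiguous, but laboratory tests and ECG are not lost if Visit 14 is meant.

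About 3 to 15 Part A participants (2 to 11 on active drug) would have an ET visit at which the two rules differ. That range rests entirely on the assumed discontinuation and attendance rates. It counts exposure to the conflict, not untested participants, and at sites that follow the schedule nobody goes untested.

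The 9.4.4 clause is a wrong criterion with little practical effect.

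Appendix 21 records that Amendment 1 moved the final laboratory tests in Appendix 2 from the follow-up visit to Visit 6/ET, so the 8.1 sentence may be a leftover. That is inference; the log does not mention 8.1.

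**What to change.** - **Section 8.1:** define the final assessment as completion of the evaluations in the Visit 6/ET column (Part A) or the Visit 12/ET column (Part B).
- **Section 9.4.4:** make the retest trigger ALT or AST at or above 3 x ULN, or total bilirubin at or above 2 x ULN. Keep the alkaline phosphatase condition only in 9.2.6. Footnote a of Appendix 2 stays as it is, and still covers smaller abnormalities and an isolated alkaline phosphatase rise.

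The cost is two protocol lines in the next amendment, with no added visit, blood draw or test. The drawback is that an amendment helps only participants still to be seen, and the 9.4.4 edit changes wording more than practice.
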